2.3. Preliminary Studies

Preliminary data obtained in the Baby Bottle study points to an unintentional overfeeding of formula fed infants. From 2012-2013 we conducted the Baby Bottle study at PBRC (NCT01762631). The purpose of the baby bottle study was to validate the remote food photography method (RFPM) for estimating energy intake for formula-fed infants. To this end, we recruited 53 men and women aged 18-80 to prepare bottles of infant formula and take photographs of the bottles simultaneously for the RFPM. The subjects were self-identified as caregivers, that is an individual who had prepared a bottle of infant formula in the past year or non-caregivers. Subjects completed two visits approximately one-week apart and prepared three bottles measuring 2fl oz, 4 fl oz, 6 fl oz and 8 fl oz, such that two trials were conducted at Visit 1 and the final trial was conducted at visit 2. The gram weights recommended for each serving of infant formula is shown in **Figure 1**, alongside the mean \pm se of actual gram weights of servings prepared by the study subjects. Of the 636 bottles prepared, 607 or 95% contained significantly more infant formula powder (by weight) than what was recommended on the package label ($p<.0001$). This finding was

Figure 1. Actual vs. recommended scoop weights

evident for each bottle size which is suggested for infant feeding from birth until 12 months of age and averaged $11 \pm 0.6\%$ (range: -24 to +140%) over-scooping across all bottles. The caloric density of a standard scoop of infant formula is 20 kcal/fl oz and therefore with this unintentional over-scooping the prepared bottles of formula had a caloric density of 22 kcal/fl oz, the caloric density often prescribed to premature infants to accelerate infant growth rate [16]. While this error may appear to be marginal for a single bottle, the error was consistent across

Infant Age	% Overfed/ meal	Energy Intake Kcal/day	Overfed (kcal/d)	Overfed (kcal/wk)
Newborn	11	350	39	273
2 months	11	480	53	371
4 months	11	500	55	385
6 months	11	590	65	455

trials. We can therefore assume that the unintentional over-scooping is consistent within an individual and the overfeeding of the infant would then compound throughout the day as multiple bottles are consumed.

These data are summarized in **Table 1**. For each bottle size the additional

formula added to each bottle, would result in an almost entire day of additional energy intake per week.

[figure not shown]

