4.5.3. Infant Formula Preparation

Participants will be asked to prepare 2 trials of 2, 4, 6, and 8 fl oz bottles of infant formula in random order. A total of 8 formula bottles will be prepared at Visit 1. For each bottle, the participant will follow their randomly assigned (Group 1 or Group 2 randomization) preparation instructions to measure the required amount of powdered formula. The participant will dispense the respective number of scoops of powdered formula into the formula bottle depending on which size bottle is being prepared. After all powdered formula is dispensed into the feeding bottle, PBRC staff will weigh the formula bottle with powdered formula only. The participant will continue following the instructions and pour water into the bottle and mix the formula. PBRC staff will weigh the formula bottle. This procedure will be repeated to assess intra- individual variability. Bottles will be weighed (to the nearest tenth of a gram) using a METTLER TOLEDO PB3001 scale, and dry formula and prepared formula weights will be recorded. Study staff who record the formula weights will be blinded to the randomization assignment and intended bottle size.

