6. DATA MANAGEMENT

6.1. Sample Size Consideration

In the Baby Bottle study, participants were asked to prepare a randomly ordered set of liquid baby formula (2, 4, 6, or 8 fl oz). Estimated proportions of participants over-scooping dry formula for bottles containing each amount were obtained from this preliminary data. A separate power analysis for the proposed study was carried out for each formula amount with the Baby Bottle estimates used to represent expected proportion of participants over-scooping dry formula when using the manufacturer preparation instructions. To ensure a well powered study, each estimate from the Baby Bottle data was reduced by an additional 15%. The most conservative results from the power analyses are presented in **Table 4** and provide a sufficient sample size to

achieve desired power when comparing the control and experimental group proportions of over-scooping for any individual formula amount as well as across all amounts. In the proposed study, we hope to see the proportion of participants over-scooping formula reduced to 50% following use of the new preparation instructions. 75 participants will be enrolled in each study group, ensuring 80% power to detect this decrease.

Table 4. Sample size calculations¹

Power (%)	Proportion over-scooped: OLD	Proportion over-scooped: NEW	N Per Group
80	0.8	0.7	294
80	0.8	0.6	82
80	0.8	0.5	39
80	0.8	0.4	23

¹*Old Proportion* represents the proportion of participants expected to over-scoop formula when using the existing instructions. *New Proportion* represents the reduced proportion of participants that are expected to over-scoop formula when using the new instructions.

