6.3. Data Analysis Plan

To address the primary aim, dry formula weights will be compared to package recommendations (i.e. 8.7 g per scoop) and classified as under-scooped, accurate scoop, or over-scooped. The proportion of bottles that are over-scooped will be compared between the two groups. Both univariate and multivariate analyses will be employed. 2x2 contingency tables with counts of participants over-scooping in each treatment arm will be constructed and chi-square tests used to compare raw proportions. This will be carried out separately for each bottle size. In addition, estimated probabilities of over-scooping for each group will be obtained from logistic regression models allowing for adjustments for bottle size and any other chosen covariates. Group-level odds ratios constructed from the estimated probabilities will be compared using two-sample t-tests. For all tests, statistical significance is defined as $p < \alpha$. Adjustments for multiple comparisons will be made when appropriate.

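### The only named test across bottle sizes, a two-sample t-test on group-level odds ratios, is not a valid test of the arm effect

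*Combined protocol and SAP*

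**What the plan says.** Section 6.3 classifies each bottle by dry powder weight and names two between-arm analyses of over-scooping.

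- Unadjusted: "2x2 contingency tables with counts of participants over-scooping in each treatment arm will be constructed and chi-square tests used to compare raw proportions". The plan adds: "This will be carried out separately for each bottle size".
- Adjusted: "estimated probabilities of over-scooping for each group will be obtained from logistic regression models allowing for adjustments for bottle size", with further covariates left open. The test that follows is: "Group-level odds ratios constructed from the estimated probabilities will be compared using two-sample t-tests".

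The section names no test of the arm coefficient and no method for repeated bottles from one person. It gives no numerical alpha and does not say which analysis is primary.

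Three other places bear on this. Section 6.1 says the sample size suffices for "comparing the control and experimental group proportions of over-scooping for any individual formula amount as well as across all amounts". Section 4.5.3 sets the data structure: "A total of 8 formula bottles will be prepared at Visit 1", two at each of four sizes. Section 2.3 says of the preliminary study: "We can therefore assume that the unintentional over-scooping is consistent within an individual".

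**The concern.** A logistic model with arm and bottle size as main effects gives one arm odds ratio. Adding an arm-by-size interaction gives four, one per size. Each is a comparison between the arms and belongs to neither, so there are no two samples to compare.

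Whoever codes this sentence must therefore substitute something else, most likely fitted probabilities, odds or logits. Those are outputs of a model that already contains arm, so they differ between arms by construction. The t-test then takes its standard error from the spread of the fitted values, which comes from bottle size and other covariates. The sampling error of the arm effect never enters.

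The stake is the pooled comparison. Section 6.1 claims power for it, and no other named test delivers it. The result could be a false claim that the new instructions work, or a missed moderate benefit, depending on a programming choice the plan does not fix.

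**Working it through.** **Alpha and the plan's own figures.** Section 6.3 gives no value for alpha, so I inferred it from Table 4 in section 6.1. The pooled-variance formula without continuity correction is

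n = [1.96·√(2·p̄(1−p̄)) + 0.842·√(p₁(1−p₁)+p₂(1−p₂))]² / (p₁−p₂)².

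For 0.8 vs 0.5, p̄ = 0.65 and n = (1.322 + 0.539)²/0.09 = 38.5, or 39. All four rows reproduce (294, 82, 39, 23). A one-sided test would give 231, 64, 31, 18. Two-sided 5% is used below.

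**Why the t-test fails, shown directly.** Take four size-specific fitted logits per arm from the main-effects model. The two sets are identical except for a shift equal to the arm coefficient b, and they share the same spread s. Then

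t = b / (s·√(2/4)) on 6 degrees of freedom, critical value 2.447.

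The test rejects when |b| > (2.447/√2)·s = 1.73·s. The standard error of b does not appear.

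- *No size differences, independent bottles, rate 0.80.* SE(b) = √(2/(600×0.16)) = 0.144. Each size logit has SE √(1/(300×0.16)) = 0.144. So b/s behaves roughly like t on 3 degrees of freedom, and P(|t₃| > 1.73) ≈ 0.18. The false-positive rate is about 18% before any within-person correlation.
- *Sizes differing.* Suppose the rates are 0.70, 0.767, 0.833 and 0.90 (equal spacing is an assumption). The logits are 0.847, 1.190, 1.609 and 2.197, so s = 0.58 and the threshold is 1.73×0.58 ≈ 1.0. A log odds ratio of 0.72 (0.80 vs 0.66) tends to fall short, while 1.39 (0.80 vs 0.50) passes.

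**Simulation with no arm effect.** There were 75 participants per arm with 8 bottles each, logistic random-intercept data and 2,000 replicates per setting (1,500 for reading 4). The documents give no intraclass correlation. Assumed: participant SD 0, 1 or 2 on the logit scale (at a rate near 0.80, SD 1 and 2 correspond to ICC of about 0.13 and 0.35); over-scooping 0.50, 0.80 or 0.89 at every size, or varying by size (0.76-0.84 or 0.70-0.90).

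| Reading of the sentence | Rejection at nominal 5% |
|---|---|
| 1. t-test on bottle-level fitted probabilities | 72-97% |
| 2. t-test on four fitted logits per arm, main effects | 18-52% if sizes do not differ; 0-17% if they do |
| 3. As 2, with arm-by-size interaction | 0-35% |
| 4. t-test on participant predictions, random-intercept model (arm only; rates 0.80 and 0.89) | 30-46% at SD 1; 11-29% at SD 2 |
| 5. Model contrast over its unclustered SE (ordinary Wald) | 5-6% at SD 0; 14-20% at SD 1; 24-30% at SD 2 |
| Participant-clustered Wald | 4.7-6.2% throughout |
| Random-intercept likelihood-ratio test | 5.1-5.3% |

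At a flat 0.80, ordinary against clustered Wald was 5.7% vs 5.6% (SD 0), 15.7% vs 5.1% (SD 1) and 30.1% vs 5.5% (SD 2).

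**With a real effect.** At 0.80 vs 0.50, readings 1, 2, 3 and 5 and the clustered test all reject in 99-100% of trials. At a moderate effect (sizes 0.70-0.90 vs 0.52-0.78, means 0.80 and 0.66), reading 2 rejects in 23.6%, 28.3% and 32.2% at SD 0, 1 and 2. The clustered test rejects in 100%, 99.0% and 89.7%.

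**Sample size after the fix.** The effective number per arm is 75×8/(1+7·ICC). At ICC 1 this is 600/8 = 75, which gives 97.7% power for 0.8 vs 0.5. At ICC 0.5 it is 600/4.5 = 133, which gives above 99.9%. Enrolment need not change.

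**The case against.** **Weight.** The logistic step is introduced as an addition to the chi-square tests. The power calculation was done for each bottle size and counts participants, so the chi-square tests match it, and they are untouched by this sentence. Section 6.3 does not say which analysis is primary, and the planned effect would be found under the readings simulated for it. All of this stands, and it confines the harm to the pooled, adjusted result under a null or smaller effect. It does not remove the harm, because section 6.1 also claims power across all sizes and this is the only test offered for that.

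**Loose wording.** The authors may have meant the t statistic that software prints for the adjusted contrast. That would be legitimate if within-participant correlation were modelled, and on that reading the remaining defect is an omission. But the text says neither, and reading 5 shows the cost of the omission.

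**The figures.** A range of 0% to 97% does not give one size for the error. Reading 1 fits the phrase group-level least, since it tests 1,200 bottle-level values. Reading 4 supposes a random intercept the plan does not name and leaves out bottle size. A common rate of 0.50 is far from the 95% seen in section 2.3 and the 89% in Aim 2. At 0.95, reading 5 falls to about 11% (SD 1) and 22% (SD 2). If the two trials per size are collapsed to one row, counted as over-scooped only when both are (an assumption), reading 5 gives about 12.5% and 19%. These points are fair and lower some figures, but every one of them stays well above 5%.

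**Conclusion.** The concern holds, with high confidence. As written, the sentence does not describe a valid test of the arm effect. Nothing elsewhere in the document repairs it, and it is the only named test that combines bottle sizes. This is a wrong method, not missing detail, and should be corrected before analysis.

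That conclusion is structural and needs no assumption. The size does: it depends on the reading coded, the participant SD, the over-scooping rate and how far sizes differ, none of which the plan settles. The most favourable reading gives about three to six times the nominal error at participant SD 1 to 2 (14-30% against 5%). The literal readings on group-level fitted values can be far too liberal or far too conservative. If over-scooping really falls from 0.80 to 0.50, the conclusion would not change; the exposure is a null or smaller effect.

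**What to change.** Delete the t-test sentence from section 6.3 and replace it with the following:

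- Test the arm coefficient of a logistic model adjusted for bottle size, accounting for the 8 bottles per participant by GEE, participant-clustered standard errors or a random participant intercept. Name one of these in advance.
- Report the adjusted odds ratio and the risk difference with 95% confidence intervals.
- If size-specific effects are wanted, add an arm-by-size interaction and test it in the same model.

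An ordinary Wald test that ignores clustering is not enough. The same rewrite should say whether this pooled test or the chi-square tests by size are primary.

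The cost is two or three sentences and the matching code, with no new data or participants. Intervals will be wider than from an unclustered model, by 1.96/z, where z matches the ordinary Wald test's null rejection rate. That is 1.96/1.476 = 1.3 at 14.0% and 1.96/1.034 = 1.9 at 30.1%, under the assumed participant SDs of 1 to 2.

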In the proposed study we will assess the literacy and understanding of individuals to follow commercially available infant formula instructions. We will collaborate with the LA CaTS Health Literacy Core to improve the reading and comprehension of the manufacturer package instruction, and we will solicit the input of caregivers and key stakeholders to inform the development of educational intervention around infant feeding. Following modification of infant formula preparation instructions, we will conduct a randomized controlled trial that will test the efficacy of the modified instructions on infant overfeeding in comparison with the manufacturer package instructions. One hundred and fifty individuals will be asked to complete one study visit during which they will be asked to measure various serving sizes of infant formula following either the manufacturer package instructions or the modified instructions. The primary outcome variable will be powdered formula weight. We have designed qualitative and quantitative research studies to test the following specific aims.

1. **Aim 1 is to evaluate parental and caregiver literacy related to the use of commercially-available instructions for the preparation of infant formula.** *Hypothesis A: the health literacy of parents and caregivers to the instructions of commercially-available infant formula is variable. Hypothesis B: More than half of the parents and caregivers studied will not demonstrate adequate understanding of the infant formula instructions of the most commonly used infant formula in the US.*
2. **Aim 2 is to improve the accuracy and precision by which individuals’ measure powdered infant formula by increasing reading ease and clarity of preparation instructions.** *Hypothesis: Improving reading ease and adding explicit pictures that convey preparation instructions will increase the accuracy and precision of scoop weight when compared to the standard instructions given on the food label. We hypothesize that preparation instructions developed with a health literacy focus (Aim 1) will reduce the proportion of over-scooped bottles from 89% to 50%.*

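### Section 6.3 gives the primary aim four bottle-size tests plus an across-size model and names no deciding test; if any one size may win unadjusted, the false-positive rate is about 14–18%, and the remedy needs no extra participants

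*Combined protocol and SAP*

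**What the plan says.** Section 6.3 classifies each dry-formula weight against the package recommendation and compares over-scooping between arms. It lists two routes to the primary aim:

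- Chi-square tests on 2x2 tables of participants. Of these it says "This will be carried out separately for each bottle size". Section 4.5.3 fixes the sizes: "Participants will be asked to prepare 2 trials of 2, 4, 6, and 8 fl oz bottles of infant formula in random order".
- In addition, "logistic regression models allowing for adjustments for bottle size and any other chosen covariates", with group-level odds ratios then compared by t-test.

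Neither route is called primary. Significance is defined as p below alpha, with alpha left as a symbol. The only statement on multiplicity is "Adjustments for multiple comparisons will be made when appropriate"; no method, family of tests or trigger is given.

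Section 6.1 claims enough participants to compare the arms "for any individual formula amount as well as across all amounts". Its target is stated as "we hope to see the proportion of participants over-scooping formula reduced to 50% following use of the new preparation instructions", and it enrols 75 per group for 80% power. For 0.8 versus 0.5, Table 4 lists 39 per group.

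Section 1 names powdered formula weight as the primary outcome variable. The Aim 2 hypothesis in the same section concerns the proportion of over-scooped bottles.

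**The concern.** Nothing in the plan stops the choice of deciding test, covariates and adjustment from being made after the data are seen. Because Section 6.1 claims power for each size as well as overall, the size-specific tests read as planned inferential claims and not as description. A positive trial could then rest on one bottle size that crossed the threshold by chance. Four separate p-values also invite the conclusion that the instructions work at some sizes and not at others, which they cannot show without a test of whether the effect differs by size.

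**Working it through.** **Inputs.** From Section 6.1: 75 per group, 0.80 versus 0.50, 80% power, and Table 4's four rows. From Sections 4.5.3 and 6.3: four sizes, one chi-square test each, all from the same participants. Assumed, because the documents do not give them: alpha of 0.05 and the within-person correlation.

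**1. Reproduce Table 4.** With p̄ = (p1 + p2)/2, the pooled-variance formula is

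n = [z(1−α/2)·√(2p̄(1−p̄)) + z(0.80)·√(p1(1−p1) + p2(1−p2))]² / (p1−p2)²

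For 0.80 versus 0.50, p̄ = 0.65, √0.455 = 0.6745 and √0.41 = 0.6403. At two-sided 0.05: (1.960×0.6745 + 0.8416×0.6403)² / 0.09 = 38.5, so 39. The other rows give 293.2, 81.2 and 22.3, so 294, 82 and 23. All four match. One-sided testing would give 231, 64, 31 and 18; a continuity correction would give 313, 91, 45 and 28. Table 4 is therefore a single test at unadjusted two-sided 0.05.

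**2. False-positive rate if any one size counts as success.** Four independent tests would give 1 − 0.95⁴ = 18.5%. The four tests share participants, so I simulated 75 per arm, one bottle per size, a true rate of 0.80 in both arms, and a latent-normal participant effect:

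| Latent correlation | At least one of four p < 0.05 |
|---|---|
| 0.3 to 0.5 | about 18% |
| 0.7 | about 16% |
| 0.85 | about 14% |
| 0.95 | about 12% |

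A separate calculation used equicorrelated test statistics and counted a pooled test as a further chance to win. It runs from 20.3% (correlation 0) to 9.4% (correlation 0.9). That correlation is between test statistics, so it is not on the same scale as the latent one.

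**3. What adjustment does to power.** Power = Φ{[|p1−p2|√n − z(1−α/2)√(2p̄(1−p̄))] / √(p1(1−p1) + p2(1−p2))}. Four-way Bonferroni uses α = 0.0125, z = 2.498. At n = 75 and 0.80 versus 0.50: (0.3×8.660 − 2.498×0.6745)/0.6403 = 1.43, power 92.3%.

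| Per group | α = 0.05 | α = 0.0125 (four tests) | α = 0.01 (five tests) |
|---|---|---|---|
| 75 (planned) | 97.7% | 92.3% | 91.1% |
| 64 (15% loss) | 95.4% | 86.8% | 85.0% |
| 57 (25% loss) | 93.0% | 81.8% | 79.5% |
| 39 (Table 4) | 80.5% | 61.6% | 58.4% |

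At 0.0125, 80% power for 0.80 versus 0.50 needs 55 per group, below the 75 enrolled.

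**4. One across-size test instead.** The same simulation, comparing each participant's share of bottles over-scooped between arms at two-sided 0.05, has a false-positive rate of about 5%. For a smaller effect, 0.80 versus 0.60, its power with 75 per group is 93–99% (latent correlation 0.7 down to 0.3) and about 88% at 0.85. Under four-way Bonferroni, one given size has 57%, and the chance of winning on any size is about 86–94% over the same 0.7 to 0.3 range.

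**The case against.** The strongest reply is that the plan already leans towards one contrast. Aim 2 states a single hypothesis about over-scooped bottles, Section 6.3 opens with one comparison of that proportion before listing methods, and it does say that adjustments will be made. No section says that one significant size means success. Section 2.3 also assumes that over-scooping is consistent within a person, which points to higher correlation and less inflation. All of this is fair, and it is why the error rate can only be stated conditionally. It does not supply a deciding test, a value for alpha or an adjustment rule.

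A reader might go further and infer that any adjustment destroys the 80% power, so that Sections 6.1 and 6.3 cannot both hold. The documents do not support that. Section 6.1 enrols 75 per group, not Table 4's 39, and at its stated effect full Bonferroni leaves 91–92%. The 62% figure belongs to the tabulated sample sizes. The 57% figure belongs to 0.80 versus 0.60, for which Section 6.1 claims no power at 75 per group: Table 4 itself asks for 82, and unadjusted power is already 76.7%. Nor does every adjustment split alpha; testing across sizes first at 0.05 costs the primary test nothing.

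**Conclusion.** The plan lacks a deciding test, a stated alpha and a multiplicity rule for its primary aim. This should be fixed, but it does not threaten the sample size. The false-positive rate of about 14–18% rests on four conditions: alpha of 0.05, no adjustment, any one size counting as success, and latent correlations of 0.3 to 0.85. It falls to about 12% at 0.95. The simulation uses one bottle per size where the protocol has two, so it shows the scale and not an exact rate.

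Power at the planned effect survives adjustment. Of the loss scenarios shown, only 25% loss combined with five-way Bonferroni falls below 80%, at 79.5%. Section 5.3 uses 15% and 25% as monitoring triggers, not as expected losses.

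**What to change.** In Section 6.3, name one primary test at two-sided 0.05: the arm contrast across all bottle sizes with the participant as the unit, for example each participant's share of the eight bottles over-scooped, compared between arms. This also handles the repeated bottles from one person. Say in Section 1 and Section 6.3 whether the primary outcome is powdered formula weight or over-scooping derived from it, so that the primary test and primary outcome agree.

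Make the four size-specific comparisons secondary with Holm adjustment, and read them together with an arm-by-size interaction. In Section 6.1, state that Table 4 is for a single test at unadjusted two-sided 0.05.

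The cost is a few sentences, with no added participants or visits. The one small downside is that a claim about a single bottle size must pass Holm.
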